10 DATA COLLECTION AND QUALITY ASSURANCE

10.1 Data Collection Forms

The primary clinical outcome for residents is found in the nursing home's routinely collected MDS assessments in their electronic medical record (EMR). Data will be extracted from the EMR by UCH IT and provided to [name] for merging, extracting participating residents and deidentifying the data.

The secondary clinical outcome (for implementation team members) will be completed within the EFCT LMS system that directly transmits the data to the PI.

Feasibility and fidelity measures will be documented as follows:

- The Resident Preferences Worksheet will be completed by the implementation team care partner delivering the IPPIs to a given resident.
- The standardized Pragmatic Checklist will be completed by the site champion for each care partner when they are conducting their first IPPI.
- Documentation of IPPIs will be completed by the implementation team care partner delivering the IPPIs to a given resident in the EMR.
- Measures of acceptability, feasibility, and appropriateness of the intervention will be collected from the implementation team members in both the EFCT LMS post-test and at the exit interview. A questionnaire will be distributed to participating implementation team members at the time of the exit interview.
- Open-ended qualitative interviews will be audio-recorded by the PI to document facilitators and barriers to implementation during the exit interview.

Each enrolled participant and implementation team member will be assigned a unique ID number to protect resident privacy. All data analysis will be with deidentified data and not include any participant's name or identifying information.

10.2 Data Management

MDS 3.0 data for all residents will be provided to the PI by UCH IT Professionals. [name] will identify participating/enrolled residents and extract distress (Section D and Section E) MDS 3.0 data at 3-months and 6-months post enrollment date and transmit data with face identifiers such as name, SSN, and HIC removed prior to statistical consultant via a secure file transfer.

Data collection forms will be provided to the site champion(s) for completion in a binder including the a) Implementation team training documentation, b) Resident Preferences Worksheet, and the c) Pragmatic Observation Checklist. For the resident preferences worksheet, site champion(s) will maintain a password protected list of the name of each resident that is enrolled into the IPPI program along with a unique ID# that is determined by the champion(s). This password protected file will be shared with the PI who will then

link the data from this worksheet to the electronic medical record data prior to deidentifying.

The statistical consultant on the project will receive de-identified data from the PI via a secure file electronic transfer.

Staff completing the EFCT will be prompted to answer questions within the EFCT LMS before and after completion of the training. These data will be extracted from Qualtrics, de-identified by the PI, and provided to the statistical consultant.

At the Exit Interviews, the PI and Project Manager will conduct a primarily qualitative interview that will help to answer secondary objectives.

Qualitative interviews will be audio-recorded, transcribed in otter.ai, and then uploaded into Dedoose, a qualitative data analysis software, and provided to the statistical consultant for coding.

10.3 Quality Assurance

10.3.1 Training

None of the NH staff serving on the implementation teams will receive human subjects research training. However, all NH staff serving on the implementation team at each of the 9 NHs will receive a series of trainings in the IPPI program before conducting the IPPI intervention. First, implementation team members will be provided information about the IPPI program. The implementation team will first complete an online training with the EFCT course. The EFCT (Emotion-focused communication training) course is a self-paced course set up through a Learning Management Service (LMS) to teach individuals strategies to better identify and manage their own feelings and those of PLWDs. Strategies taught in the course are designed to build individuals' emotional communication skills, forge stronger relationships and provide more positive care experiences for care partners and PLWD alike. Second, the implementation team will complete the provided IPPI activity training videos. These training videos demonstrate less effective and more effective dementia communication skills and staff to the use of simple, "plug and play" resources to deliver the IPPI activities during their normal daily workflow. Care partners will also be provided a body of IPPI activity manuals with checklist of steps, 60+ different IPPI protocols that address all 16 MDS preferences in Section F, sample letters/scripts introducing the IPPI to family and staff, and communication tips sheets. Each IPPI activity has a corresponding toolkit with instructions and supportive conversation prompts that consist of an introduction, middle, and conclusion section. The IPPI program has been explicitly designed for PLWD who are experiencing symptoms of distress.

Each care partner that is trained will first observe the site champion completing an IPPI with a resident and then will be shadowed by the site champion upon implementation of their first IPPI. Feedback will be provided to ensure protocols are being followed.

In addition, the project manager will provide virtual coaching throughout the pilot grant period through monthly calls and as needed.

10.3.2 Quality Control Committee

A formal quality control committee will not be assembled, however monthly check-in calls with the site champions with the participating NHs will serve as an opportunity to monitor quality and address concerns in implementation. The Project Manager will lead these meetings and ask participants to provide an update on implementation at each meeting to ensure the project is moving forward as anticipated.

10.3.3 Metrics

The MDS 3.0 data will serve as our primary outcome measure. NH providers have dedicated MDS nurses who have been trained how to correctly input the MDS data as it also provides the algorithm for reimbursement. Data from our secondary outcome will be provided by the implementation team before and after they engage with the emotion-focused communication training. The Qualtrics questionnaire has been set so individuals cannot skip any question. There is a “prefer not to answer” option offered for every question to ensure all questions are reviewed and that participants can skip any question.

10.3.4 Protocol Deviations

During the monthly calls the PI will take notes of any ongoing project barriers or facilitators which will be explored in the Exit Interviews as well, with this any deviations from the protocol for a given NH will be documented. These documented deviations will be shared with the project data manager/statistical consultant to determine impact on analyses and inclusion of data. All deviations will also be compiled to report as lessons learned from the pilot project to inform submission of a future full-scale Stage IV effectiveness ePCT study.

10.3.5 Monitoring

Monthly check-in calls with the nine participating NH site champions will serve as a monitoring function for this pilot grant. The Project Manager will check-in with each site during these calls to ensure each is following the agreed upon protocol for enrollment, training, shadowing, and implementation. Data collection forms will also be reviewed every 3 months by the Project Manager, to support project implementation.

11 **PARTICIPANT RIGHTS AND CONFIDENTIALITY**

11.1 Institutional Review Board (IRB) Review

This protocol and waiver for consent and any subsequent modifications will be reviewed and approved by Advarra, Inc.

11.2 Informed Consent Forms

Consent:

Nursing Home Residents: There will be no randomization process for this feasibility trial.

We are requesting a waiver of consent for resident participation in the study. This includes not only those that are exposed to the IPPI program itself, but for the release of EHR data for all NH residents in the study sites, regardless of participation/eligibility. The latter is because it would be challenging for the UCH IT staff to create a cohort-specific data extract for the project. We believe the waiver of informed consent is justified for the following reasons.

First, the research involves no more than minimal risk to subjects. Prior research has indicated there is minimal risk because this is a preference-based activity for the resident and should be a positive experience. The types of activities we are asking staff to engage residents in are usually done as part of standard care, but in a group setting.

Second, the research could not be practicably carried out without the requested waiver. It would not be practicable for care partners to seek informed consent from either the NH resident living with dementia or their legally authorized representative because the IPPI is a clinical process implemented to address a clinical need. For example, the moment a resident starts to be physically or verbally abusive to a staff member during care they need to have the ability to immediately start an IPPI activity. The IPPI activities would be integrated into the care process to address a clinical need. We do not think that residents or their legally authorized representative would object if they knew of the waiver and its intent in facilitating the research. We believe that most people would prefer to engage in activities they find meaningful and enjoyable on a one-to-one basis.

Third, we need to use identifiable private information and the research could not practicably be carried out without using such information in an indefinable format. Because we will need to link individual level data from multiple data sources (e.g., MDS and EMR) we will work with UCH IT to send the PI a crude dump of their system and the PI will link, deidentify the data and send to the statistical consultant.

Fourth, we do not think the waiver has the potential to cause adverse consequences as it involves engagement with a care partner in a preferred important activity. We are not allowing for the opportunity to obtain clinical consent but relying upon the staff clinical judgement to identify when the resident would benefit from an IPPI activity.

Fifth, the resident's legally authorized representative will be provided with information about the IPPI program upon enrollment via phone call or email and told that their loved one/client is involved in the IPPI program to remediate the communication of distress. We can and plan to share information about the findings of the study with each UCH site.

Implementation Team as Study Subjects:

We will explain the IPPI program to staff at each UCH location and seek volunteers to be a part of the implementation team who will roll out the program (they will not be consented as study subjects). We will invite them to be trained in delivering the IPPI and support them as needed during the duration of the project.

We will seek to consent staff to complete a semi-structured group exit interview at the end of the study. We request a waiver of documentation of consent for this activity. This will be sought by either the project manager or PI conducting the interview because we will be conducting the interviews via telephone or Zoom. There is minimal risk as we will be asking implementation team members to tell us about the implementation facilitators and barriers they experienced.

11.3 Participant Confidentiality

We are requesting a full HIPAA waiver in order to utilize PHI for both recruitment and outcome data. Staff need to access the MDS data to identify eligible residents and the PI plans to receive an identifiable data dump from UCH. The use of identifiable data involves no more than minimal risk to the privacy of individuals for the following reasons. First, UCH IT will send the PI the data through a secure file transfer that is password protected. Second, once the PI is able to link the data sets, identifiers will be destroyed prior to sending to the statistical consultant via a secure file transfer that is password protected. Third, PHI will not be used or disclosed to a third party except as required by law. Fourth, the research could not be practicably conducted without the full HIPAA waiver because UCH staff could not be able to identify eligible residents without the waiver. Fifth, the research could not be practicable conducted without the ability to link individual data from multiple data sets (e.g., MDS 3.0 and EMR).

We will plan for an individualized report to each NH community with results based on their staff and residents. In addition, we will offer to present aggregated findings at town hall sessions, resident council, and family council meetings. Information will not be released without written permission of the participant, except as necessary for monitoring by IRB, the sponsor or persons working on behalf of the sponsor (i.e. IMPACT research study staff, the DSMB and/or Safety Officer), the FDA, the NIA and its authorized representatives, and the OHRP.

11.4 Study Discontinuation

The study may be discontinued at any time by the IRB, the NIA, the IMPACT Collaboratory, the OHRP, or other government agencies as part of their duties to ensure that research participants are protected.

12 ETHICAL CONSIDERATIONS

All study procedures and protocols will be pre-approved by the Advarra, Inc. and will meet all ethical requirements for Human Subjects Research.

13 COMMITTEES

N/A

14 PUBLICATION OF RESEARCH FINDINGS

Publication of the results of this trial will be governed by the policies and procedures developed by the Steering Committee. Any presentation, abstract, or manuscript will be made available for review by the IMPACT Collaboratory prior to submission. Publication of the results of this pilot study will be governed by the policies and procedures developed by the IMPACT Collaboratory.

16 SUPPLEMENTS/APPENDICES

While any member of the implementation team can complete these forms, we anticipate the champion(s) being primarily responsible. We will ask that the champion(s) submit data to the research team in batches with the 3 month and 6 month electronic data. These forms can be scanned and emailed or faxed to the project manager, [name] via encrypted email at [contact] or private fax at [contact].

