6.1 Schedule of Evaluations

Assessment	Pre-enrollment	Baseline, Enrollment (Day 0)	Each IPPI (2x a week for 180 days)	3-month Assessment (~Day 90)	6-month Assessment (~Day 180)	Post Intervention Trial
Organizational Readiness for Implementing Change (ORIC)	X					
MDS 3.0 data of residents BIMS scores and Section D and E Responses (rolling ; each resident assessed for enrollment to serve as baseline assessment, 3-mon, and 6-mon)	X	X		X	X	
Identify Implementation team (Y/N)	X					
Virtual Coaching session attendance (Y/N)	X			X	X	
Emotion-Focused Communication Training (EFCT) completion (Y/N)	X					
Emotion-Focused Communication Training (EFCT) pre and post-test (knowledge, efficacy)	X					
IPPI Training (watching 2 videos) completed (Y/N)	X					
Resident Preferences Worksheet (rolling)		X	X	X	X	
Care Plan Documentation (Y/N)		X	X	X	X	

Fidelity Assessment with Pragmatic Checklist (observation of 1st IPPI between each resident and implementation team member delivering IPPI)			X (1 st IPPI only)			
Exit Interview (communication, acceptability, feasibility, appropriateness, facilitators, and barriers)						X
Troubleshooting (count of contacts)	X	X	X	X	X	
Intervention Withdrawal form			X			
Adverse Events form			X			

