6.2 Description of Evaluations

6.2.1 Pre-enrollment

These evaluations occur prior to enrollment of NH residents to the intervention.

Organizational Readiness

To understand each NH's organizational readiness for the intervention, each implementation team member will be asked to complete the ORIC assessment.

Identifying subjects (Screening)

UCH site champions will be trained to identify eligible residents in each community using MDS 3.0 BIMS data (score of 0 to 12) and documentation of distress as indicated by a non-zero response in Section D on PHQ-9 items of anhedonia, sad mood, poor self-esteem, poor appetite, or restlessness or a non-zero response on a Section E behavior.

Identification of eligible residents will occur on a rolling basis, following completion of a given resident's quarterly or annual MDS 3.0. Upon review of MDS 3.0 assessments at the care planning meeting, if a resident triggers for cognitive impairment and distress, the person will be identified as eligible for the IPPI program. As a rolling process, site champion(s) and care partners will identify any newly eligible residents who have completed their quarterly or annual MDS 3.0 assessments and trigger for cognitive impairment and distress. This process will likely result in adding 3-8 residents per month for 3-4 consecutive months.

Baseline MDS 3.0 assessments (includes BIMS and Distress data) and two subsequent MDS 3.0 assessments (at approximately 3 and 6 months), along with EMR data that document the IPPIs will be provided to PI approximately half-way and at the completion of the project by the UCH corporate IT officer via a secure file transfer service. The half-way point will be when all enrolled residents are past their 3-month post IPPI initiation. The completion of the project will occur 6 months post IPPI initiation. Data for all residents will be provided and the PI will link the MDS and EMR data, extract residents engaged in the IPPI project, deidentify, and add a unique ID number for each participant prior to providing data to the Statistical Consultant, [name] via a secure file transfer service.

Implementation team training

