6.2.2 Enrollment, Baseline, and/or Randomization

Enrollment

There will be a waiver of consent for all residents enrolled in the program. Upon identification of eligibility, the implementation team uses the Resident Preferences Worksheet to identify next steps. This will be a rolling process as individuals are identified as eligible to participate. Each enrolled individual will have a Worksheet completed at their specific time of enrollment. In this Worksheet, members of the implementation team will identify the resident's important preferences and identify matching IPPI protocols that can be used. They will also identify the behavior they hope to target with the IPPI intervention. A copy of the care plan will be obtained to ensure that the targeted behavior is addressed. The PI will collect this Worksheet from champions to determine whether or not the IPPI protocols were appropriately matched to important resident preferences as a measure of implementation fidelity every three months.

Baseline Assessments

The baseline assessment for residents will be their most recent MDS 3.0 (either

annual or quarterly). The BIMS and Section D/Section E responses will be provided to the PI for each enrolled resident by the UCH IT professionals. These data will include the targeted mood or behavior selected by care partners at enrollment. The type of mood or behavior item being targeted will be different for each resident (e.g., wandering for one, verbal behavior for another).

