The primary clinical outcome will be reports of distress as rated in the residents' MDS 3.0 annual or quarterly assessments in Section E and Section D (Saliba & Buchanan, 2009). These items will also be rated by the implementation team care partner delivering the intervention. These data will be collected at baseline (to determine eligibility) and at 3-months and 6-months post-intervention enrollment. The items in Section D and Section E are validated standardized items used to assess all NH residents in the United States receiving funding from the Centers for Medicare and Medicaid Services. Section D depression item responses are drawn from the widely used and validated PHQ-9 (Kroenke et al., 2001; anhedonia, sad mood, poor self-esteem, poor appetite, or restlessness). The items ask *“Over the past 2 weeks, have you been bothered by any of the following problems?”* and then if the resident responds “yes” they are asked *“About how often have you been bothered by this?”*. Item level scores are 0 (*did not occur*), 1 (2-6 days), 2 (7-11 days), or 3 (12-14 days). The Section E behavior items have been used as a valid indicator of behavioral distress (Saliba & Buchanan, 2009). Items include the presence of verbal, physical or other behavior symptoms directed toward others, rejection of care, and wandering. For section E, each behavior is rated with a 0 (*did not occur in the past week*), 1 (*occurred 1-3 days in the past week*), 2 (*occurred 4-6 days*) or 3 (*occurred daily*). For each resident care partners will have designated a targeted mood or behavior item selected for improvement and assessed via MDS data. The targeted mood or behavior selected by the care partner at baseline will be reassessed at 3-months and 6-months and recorded as 0 = *stayed the same as baseline* (e.g., score on MDS 3.0 baseline assessment equals score on MDS 3.0 follow-up assessment), 1 = *got better* (e.g., score on

MDS 3.0 baseline assessment is better (lower) than the score on the MDS 3.0 follow-up assessment), or 2 = *got worse* (e.g., score on MDS 3.0 baseline assessment is worse (higher) than the score on MDS 3.0 follow-up assessment) for our primary, person-centered clinical outcome. The type of mood or behavior item being tracked will be different for each resident (e.g., wandering for one, verbal behavior for another)

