9.4.1 Primary outcome

The primary clinical outcome will be reports of distress as rated in the residents' MDS 3.0 annual or quarterly assessments in Section E and Section D (Saliba & Buchanan, 2009). These items will also be rated by the implementation team care partner delivering the intervention. These data will be collected at baseline (to determine eligibility) and at 3-months and 6-months post-intervention enrollment. For each resident, a targeted mood or behavior item selected for improvement and assessed via MDS data will be used as the primary outcome. The targeted mood or behavior will be recorded as 0 = *stayed the same as baseline* (e.g., score on MDS 3.0 baseline assessment equals score on MDS 3.0 follow-up assessment), 1 = *got better* (e.g., score on MDS 3.0 baseline assessment is better (lower) than the score on the MDS 3.0 follow-up assessment), or 2 = *got worse* (e.g., score on MDS 3.0 baseline assessment is worse (higher) than the score on MDS 3.0 follow-up assessment) for our primary, person-centered clinical outcome at 3-months and 6-months post

intervention enrollment. The type of mood or behavior item being tracked will be different for each resident (e.g., wandering for one, verbal behavior for another).

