***email address will be used to identify if individual completed the Emotion Focused Communication Training**

IPPI Program – Resident Preferences Worksheet

Site champion(s) will maintain a password protected list of the name of each resident that is enrolled into the IPPI program along with a unique ID# that is determined by the champion(s). This password protected file will be shared with the PI who will then link the data from this worksheet to the electronic medical record data prior to deidentifying.

After completing a resident's preference assessment, identify and record their most important preferences in the column "Important Preferences." Next, review the list of IPPI protocols then record the protocols that match the resident's important preferences in the "Matching IPPIs" column. Review the list of matching IPPIs with the implementation team member(s) that will be facilitating the activity with the resident and let them chose which IPPI activities (1-2) they are most comfortable doing. After they've chosen the IPPI activities, record their selection in the "IPPIs Selected" column. Identify one or more resident behaviors that are the target outcome for the intervention as indicated on the MDS Section E. Finally, note if the resident completed the project and if there were any adverse events.

Resident Unique ID#	Important Preferences	Matching IPPIs	IPPIs Selected by implementation team	Supplies Needed Location	Which targeted behavior(s) do you hope the IPPI will remediate? Check all that apply	Did the resident complete the IPPI Project? Yes No If no, why did the individual not complete the project?	Did the resident have any adverse events? Yes No If Yes, complete Serious Adverse Event Report Form
	•	•	•	○	 Physical behavioral symptom  Verbal behavioral symptom  Other behavioral symptom  Rejection of Care  Wandering  Depressive Mood Symptoms	○	○

Observation Checklist of Fidelity to IPPI Protocol conducted by Champion

Did the person delivering the IPPI do any of the following?

1. Yes No N/A Introduce self to resident
2. Yes No N/A Introduce IPPI activity to resident
3. Yes No N/A Consider possible distractions (background noise, visual/tactile)
4. Yes No N/A Check that individual could hear or was wearing hearing aids if applicable
5. Yes No N/A Interrupt resident in the middle of a visit (reverse coded)

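### The target item behind the primary outcome is to be chosen at enrollment, but no procedure makes that choice single, dated and on file before follow-up

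*Combined protocol and SAP*

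**What the plan says.** **Definition.** Section 9.4.1: "For each resident, a targeted mood or behavior item selected for improvement and assessed via MDS data will be used as the primary outcome". It is coded same, better or worse at 3 and 6 months, and Section 9.5 reports the aggregate percentages.

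**Time of choice.** Section 6.2.2: "Each enrolled individual will have a Worksheet completed at their specific time of enrollment". The same section says of the baseline data: "These data will include the targeted mood or behavior selected by care partners at enrollment". Section 9.1: "The targeted mood or behavior selected by the care partner at baseline will be reassessed at 3-months and 6-months".

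**The form.** The target is entered on the Resident Preferences Worksheet in Appendix A, whose instruction reads: "Identify one or more resident behaviors that are the target outcome for the intervention as indicated on the MDS Section E". The target column has five behavior boxes and one box for depressive mood symptoms, and invites staff to tick all that fit.

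**Later handling.** The schedule in 6.1 marks the worksheet at baseline, at each IPPI, at 3 months and at 6 months. Section 16 asks champions to "submit data to the research team in batches with the 3 month and 6 month electronic data". Section 6.2.1 times the first electronic transfer: "The half-way point will be when all enrolled residents are past their 3-month post IPPI initiation". Section 6.2.2, however, has the investigator collect the worksheet every three months, and Section 10.3.5 has the project manager review the forms every 3 months.

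**The concern.** The trial has no control arm, and the percentages improved, unchanged and worsened are its only resident-level clinical result. Section 9.2 says the findings will inform the power of a larger trial. Those percentages depend on which item is scored for each resident.

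The staff who choose the target also deliver the program. Sections 9.1 and 9.4.1 have the delivering care partner rate the same items as well, and champions work with MDS data to find eligible residents. The people holding the form may therefore know the follow-up scores. If the scored item can be picked, narrowed or changed at that stage, items that happened to fall are favored and the improved share rises without any program effect. With no dated record, nobody could later show whether this happened.

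**Working it through.** The documents give no power, alpha or effect figure for the resident outcome, so there is no stated number to reproduce. The check compares the sections, works out a timeline, and sizes the possible bias under stated assumptions.

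**1. Is the target unique and verifiable on the form?**
- Section 9.4.1 needs one item. The worksheet allows several, and Section 9.5 speaks of each resident's targets in the plural.
- Five Section D items qualify (Sections 4 and 9.1), but the form has one mood box. A tick there does not say which item is scored.
- The target column has no field for date, MDS item or baseline score. No section forbids, logs or dates a change.
- The care plan copy (6.2.2, Table 1) is checked for mention of the target. It too is marked at later time points in 6.1, as a Y/N entry, and is not named as the outcome source.
- Appendix A points to Section E, whereas Sections 3, 9.1 and 9.4.1 allow a mood or a behavior item. No section requires the target to be non-zero at baseline.

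**2. When does the team receive the form?** Assume MDS assessments at exactly 3 and 6 months, even enrollment, and an enrollment window of E = 3 or 4 months (Sections 2.2 and 3).
- Sections 16 and 6.2.1: first batch at E + 3, so month 6 (E = 3) or month 7 (E = 4). Every 3-month MDS is then due. With E = 4, the 6-month MDS is also due for (7 − 6)/4 = 25% of residents; with E = 3, for none.
- Sections 6.2.2 and 10.3.5, read as a calendar cycle: the wait is at most 3 months, so a form is collected at or before that resident's own 3-month MDS.
- The two arrangements give opposite answers for the 3-month outcome.

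**3. How large could the bias be?** All inputs here are assumptions: k candidate items per resident, each improving independently with probability p whatever the program does, and a fraction r of residents re-targeted to their best item.

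Share improved = p + r × [1 − (1 − p)^k − p]

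With p = 0.40, a target fixed at enrollment gives 40%. Otherwise:
- k = 2: 1 − 0.6² = 0.64. r = 0.10 gives 0.40 + 0.10 × 0.24 = 0.424. r = 1 gives 0.64.
- k = 3: 1 − 0.6³ = 0.784. r = 0.10 gives 0.40 + 0.10 × 0.384 = 0.438. r = 1 gives 0.784.

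For 108 residents, the shift at r = 0.10 is 108 × 0.024 = 2.6 to 108 × 0.0384 = 4.1 residents. At r = 1 it is 25.9 to 41.5.

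For p from 0.20 to 0.50:
- r = 0.10: 21.6% to 52.5% (k = 2), or 22.9% to 53.8% (k = 3).
- r = 1: 36% to 75% (k = 2), or 48.8% to 87.5% (k = 3).

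**The case against.** The strongest reply is that the plan does fix the target at entry. Sections 6.2.2 and 9.1 say so, Section 7 makes a completed worksheet part of the definition of enrollment, and no section permits a change. Section 3 even gives a basis for choosing: the mood or behavior item most distressing to the resident. A reader might infer from the schedule that the target is reopened at each visit. The documents do not support that. Later marks have ordinary explanations: rolling enrollment, the adverse-event column (7.3.1), and the completion and withdrawal column (7.3.1 and 8). What stands is that nothing limits later entries to those columns.

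A reader might also infer that the team sees the target only after the 3-month MDS. Sections 6.2.2 and 10.3.5 contradict this, although the purpose given in 6.2.2 is checking preference matching. The conflict with Section 16 stands. Even the later arrangement would put most forms in hand before the 6-month MDS, but no section makes the first form received final, and the 3-month score would already exist.

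A further inference is that residents eligible on mood alone are forced onto a Section E target scored 0, which cannot improve. The mood box on the same form largely answers this. Targets scored 0 could also be counted from the baseline MDS data where the item is known. No section suggests how many there would be.

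Finally, resident outcomes are descriptive in a feasibility pilot, so no hypothesis test is at risk. Section 6.2.3 also scores change on each Section D and E item, so target results could be set against all items. That would give context, but would not show which item was chosen at enrollment.

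**Conclusion.** The concern holds in a limited form. The time of selection is stated; a unique, dated record that would prove it before follow-up is missing, and the sections on form collection disagree. The risk is upward bias in the reported improved percentage, not an inflated type I error.

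Its size cannot be known from the documents. Under the assumptions shown, limited re-targeting moves 40% by about 2 to 4 points. The 64% to 78% figures require every resident to be re-targeted to the best of two or three independent items, and are an upper bound, not an expectation. Nothing suggests that staff intend to change targets. The change is still worthwhile because it is cheap and makes the primary outcome checkable.

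**What to change.** 1. **Section 6.2.2 and 9.4.1.** At enrollment, before the first IPPI session, the champion records resident ID, date, one specific Section D or E item and its baseline score, and sends this to the project manager by the encrypted email or private fax already provided in Section 16. That entry is the only target scored in 9.4.1. Any later change is logged but not used.
2. **Section 6.1.** State that worksheet entries after baseline are limited to the completion or withdrawal column and the adverse-event column. Reconcile Sections 6.2.2, 10.3.5 and 16 on when forms are collected.
3. **Appendix A.** Refer to MDS Section D or E instead of Section E alone, ask for one primary item in place of multiple ticks, list the mood items separately, and require the scored item to be non-zero on the baseline MDS.

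Cost: about 105 to 110 short messages, one per enrolled resident, plus protocol and form wording. No new assessments are needed.
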